#### **7.3.5. Largest Percentage Reduction in Sum of Diameters of Target Lesions**

For each subject in the FAS population with target lesions at baseline, target lesion sizes will be measured by sum of diameters. The best percentage change from baseline, defined as the largest decrease in target lesion size for each subject, will be summarized descriptively, and a waterfall plot of the best percentage change will be generated.

Per RECIST criteria, target lesions considered "too small to measure" will be assigned a default value of 5 mm for purposes of this analysis. Likewise, target lesions identified as "not present" at postbaseline assessments will be assigned 0 mm for this analysis. In the event a target lesion is unaccounted for in a particular postbaseline timepoint (ie, assessment missing or NE), then the overall sum of diameters for target lesions will not be evaluable for that postbaseline timepoint.

#### **7.3.6. Percentage Change in Sum of Diameters of Target Lesions Over Time**

For each subject in the FAS population with target lesions at baseline, target lesion sizes will be measured by sum of diameters. The percentage change in sum of diameter of target lesions over time will be listed and a spider plot will be generated.

#### **7.3.7. Progression-Free Survival**

Progression-free survival is defined as the length of time between the baseline visit (Day 1) and the earlier of death or PD as assessed by RECIST v1.1 and mRECIST v1.1. Date of death will be determined using the Death Report CRF.

Censoring for PFS will follow the algorithm outlined in [Table 7](#) which is based on the FDA – Guidance for Industry: Clinical Trial Endpoints for the Approval of Cancer Drugs and Biologics (FDA 2007).

Kaplan-Meier curves for PFS will be presented by cohort-specific tumor types. The KM estimate of median PFS will be presented with its 95% CI. The 95% CI will be calculated using the Brookmeyer and Crowley's method ([Brookmeyer and Crowley 1982](#)).

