2.2.2. Secondary Endpoints

- ORR, defined as the percentage of subjects having CR or PR, will be determined by investigator assessment of radiographic disease assessments per RECIST v1.1 and mRECIST v1.1.
- DOR, defined as the time from the earliest date of disease response (CR or PR) until earliest date of disease progression or death due to any cause, if occurring sooner than progression, will be determined by investigator assessment of radiographic disease assessment per RECIST v1.1 and mRECIST v1.1.
- DCR, defined as the percentage of subjects having CR, PR, or SD, will be determined by investigator assessment of radiographic disease assessments per RECIST v1.1 and mRECIST v1.1.
- Duration of disease control (CR, PR, and SD) as measured from first report of SD or better until disease progression or death from any cause, if occurring sooner than progression, will be determined by investigator assessment of radiographic disease per RECIST v1.1 and mRECIST v1.1.
- PFS, defined as the time from the start of combination therapy until the earliest date of disease progression or death due to any cause, if occurring sooner than progression, as determined by investigator assessment of objective radiographic disease assessments per RECIST v1.1 and mRECIST v1.1.
- OS determined from the start of combination therapy until death due to any cause. Survival analyses will occur at 1-year, 2-years, and at the end of the study.
- Safety and tolerability will be assessed by monitoring frequency, duration, and severity of AEs.

[REDACTED]

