6.4.3. Survival Follow-Up

Once a subject has received the last dose of study treatment, confirmed disease progression, or starts a new anticancer therapy, the subject moves into the survival follow-up period and should be contacted by telephone, email, or visit at least every 12 weeks (+ 7 days) to assess for survival status until death, withdrawal of consent, or the end of the study, whichever occurs first.

Note: As of Protocol Amendment 5, survival follow-up will no longer be required beyond the last safety follow-up visit for subjects who have confirmed disease progression or start a new anticancer therapy. The last survival follow-up data will be recorded in the eCRF at the time of the last safety follow-up visit. The last study visit will be the last safety follow-up visit.

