**Table 7: Evaluation and Censoring of Progression-Free Survival**

Situation	Outcome	Date of Progression or Censoring
No baseline tumor assessments	Censored	Date of Day 1
No valid postbaseline response assessments	Censored	Date of Day 1
Progression documented between scheduled response assessments	Progressed	Date of first overall response of PD
No progression	Censored	Date of last valid radiologic assessment (not NE and not missing)
Study discontinuation for undocumented progression	Censored	Date of last valid radiologic assessment (not NE and not missing)
Study discontinuation for toxicity or other reason	Censored	Date of last valid radiologic assessment (not NE and not missing)
New anticancer treatment started	Censored	Date of last valid radiologic assessment (not NE and not missing) on/before starting a new anticancer treatment. (Date of PD assessment if the new anticancer treatment started after PD.)
Death before first progressive response assessment	Progressed	Date of death
Death between adequate response assessments	Progressed	Date of death
Death or progression after more than 1 missed assessment	Censored	Date of last valid radiologic assessment (not NE and not missing) before death

NE = not evaluable.

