### 7.3.8. Overall Survival

Overall survival is defined as the interval between Cycle 1 Day 1 and the date of death due to any cause. Date of death will be determined using the Death Report, the Survival Follow-Up, and the Subject Status CRFs. Subjects who are lost-to-follow-up or still alive at the time of analysis will be right-censored at the earlier of the date the subject was last known alive and the clinical data cutoff date for the analysis. The last known alive date is defined as the later of the last study visit and the date the subject was last known alive from the Survival Follow-Up and Subject Status CRFs.

Kaplan-Meier time to event curves will be presented by treatment groups. Median survival will be estimated using the KM method. Kaplan-Meier estimates of 1-year and 2-year survival probabilities will be provided. Confidence intervals for median survival time will be calculated using the method of Brookmeyer and Crowley (1982).

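### PFS and DOR: the SAP names one death source for PFS but three for OS, and the last row of Table 7 gives no usable censoring date for progression after missed scans

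*SAP*

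**What the plan says.** Protocol 2.2.2 gives the endpoint as "PFS, defined as the time from the start of combination therapy until the earliest date of disease progression or death due to any cause". SAP 7.3.7 uses the same event, and Table 7 counts "Death before first progressive response assessment" as an event on the date of death.

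The two survival-type endpoints name different sources for that date. For PFS (SAP 7.3.7): "Date of death will be determined using the Death Report CRF". For OS (SAP 7.3.8): "Date of death will be determined using the Death Report, the Survival Follow-Up, and the Subject Status CRFs". Nothing in the SAP reconciles them. SAP 7.3.3 sends DOR to the PFS censoring algorithm. Duration of disease control (SAP 7.3.4) also ends at death but names no source.

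The last row of Table 7 describes the situation "Death or progression after more than 1 missed assessment". Its outcome is Censored, and its date is "Date of last valid radiologic assessment (not NE and not missing) before death".

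**The concern.** There are two separate drafting faults.

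**Death source.** Naming three forms for OS suggests that the authors thought one form might not capture every death. The documents do not say that a Death Report is completed for each death. If a subject without PD or new therapy dies and the death is on only one of the other two forms, the PFS rule as written does not find it. The subject is dead in OS and censored at the last valid scan in PFS, although no Table 7 rule intends that. Such censoring is informative, because the subject is censored precisely because of a failure.

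**Table 7, last row.** One row covers two situations, but its date is anchored to only one of them. For a progression found after a gap, the programmer has either no date or a date on the wrong side of the gap. The subject is then credited with progression-free time that nobody observed.

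Both faults push Kaplan-Meier estimates of PFS and DOR upward.

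**Working it through.** The plan states no event count, power or median for PFS or OS, so there is no figure of its own to reproduce.

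**1. Who can be affected by the death source**

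Protocol 6.4.3 says: "Once a subject has received the last dose of study treatment, confirmed disease progression, or starts a new anticancer therapy, the subject moves" into survival follow-up. That includes subjects off treatment without PD. Protocol 7.11.2 allows deaths to be learned by phone contact, patient records or public records. A death that still counts for PFS can therefore first come to light in survival follow-up. Deaths after PD or after new therapy do not matter here, because PFS has already ended or been censored.

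**2. Size of the death-source fault (illustration only)**

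Assumptions, none of them in the documents: exponential PFS with a median of 4.0 months; deaths without PD make up 20% of PFS events; between none and half of those lack a Death Report.

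- Share of events lost, *f* = 0.20 × (0, 0.25, 0.50) = 0, 5%, 10%.
- If these are censored at the event time, the hazard falls by the factor (1 − *f*). The median is 4.0/(1 − *f*) and 6-month PFS is 0.5^(1.5 × (1 − *f*)), because 6/4.0 = 1.5.

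| Events lost | Median (months) | 6-month PFS |
|---|---|---|
| 0% | 4.0 | 0.5^1.5 = 35% |
| 5% | 4.0/0.95 = 4.2 | 0.5^1.425 = 37% |
| 10% | 4.0/0.90 = 4.4 | 0.5^1.35 = 39% |

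Table 7 would censor at the last scan rather than at the event time. A simulation of 200,000 subjects on an 8-week scan grid gives medians of 4.16 (5% lost) and 4.36 (10% lost), which is close to the table.

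Wider assumptions: deaths are 10-30% of PFS events, and 10-50% of them lack a Death Report.

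- Lost per 50 events: from 50 × 0.10 × 0.10 = 0.5 to 50 × 0.30 × 0.50 = 7.5.
- Simulated medians: 4.03 to 4.60 months where the true median is 4.0, and 2.02 to 2.26 where it is 2.0.

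**3. Table 7, last row, applied literally**

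The scan interval is 8 weeks (Protocol Table 10, imaging footnote). The last scan before the gap is at week 8 in each case.

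| Subject | As written | Dated before the missed assessments |
|---|---|---|
| Weeks 16, 24 and 32 missed, death at week 36 | week 8 | week 8 |
| Weeks 16 and 24 missed, PD at week 32, death at week 40 | week 32 (the PD scan) | week 8 |
| Weeks 16 and 24 missed, PD at week 32, alive | no date defined | week 8 |

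In the second case the difference is 32 − 8 = 24 weeks. If that subject also has the repeat scan 4-6 weeks after first PD (Protocol 7.7.1), the last valid scan before death is at week 36-38, which is after documented PD. The outcome is Censored in every cell. The death half of the row works as it stands.

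**The case against.** The strongest reply is that the death-source effect depends on CRF practice that the documents do not show. If sites complete a Death Report for every death, nothing is lost. This stands, and it is why the range above starts at zero.

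The exposed group is also narrow. Subjects off treatment without PD continue to be imaged (Protocol 6.4.2). The synopsis moves subjects to survival follow-up only after confirmed PD or new therapy, which is narrower than 6.4.3. Deaths after more than one missed assessment are censored anyway. Since Amendment 5, disease and survival follow-up stop at the last safety visit. All of this limits the reach of the fault but does not remove the mismatch.

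A reader might infer that any subject who is dead in OS and censored in PFS reveals an error. The documents do not support that. Table 7 produces this combination on purpose, for example in the row "New anticancer treatment started" and where there is no baseline or no valid postbaseline assessment.

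A reader might also infer that the Table 7 row adds to the PFS/OS conflict. It cannot, because its outcome is Censored whichever date is used. Nor is the date always the PD scan: it can be later, or undefined.

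Finally, PFS and DOR are secondary and are summarised by Kaplan-Meier without a hypothesis test. That is correct and limits the weight of the point.

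**Conclusion.** Both faults are in the SAP text, and they are independent of each other.

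- **Death source.** It can make a subject an OS event and a PFS non-event, contrary to the SAP's own definition, but only for deaths without prior PD or new therapy that have no Death Report. The documents neither show nor exclude such deaths, so the effect may be zero. Under the stated assumptions (0-10% of events lost, exponential PFS, 4.0-month median) the median becomes 4.0-4.4 months and 6-month PFS rises from 35% to at most 39%.
- **Table 7, last row.** The censoring date is undefined or too late for the progression half. In the worked case it is 24 weeks too late. The number of such subjects cannot be estimated from the documents.

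The Simon rules and the Bayesian probability-of-success rules use response data, so no go/no-go decision, error rate or sample size changes. The point merits correction because following either rule as written can give a wrong or undefined secondary result.

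**What to change.** 1. In SAP 7.3.7, take the date of death from the Death Report, Survival Follow-Up and Subject Status CRFs, as 7.3.8 does. Derive it once and use it for PFS, DOR, duration of disease control and OS. State this in 7.3.3 and 7.3.4 as well.
2. In the last row of Table 7, replace the closing words *before death* with *before the missed assessments*, so that one date serves both halves of the row.

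The cost is a few words in the SAP and one shared derived variable; no new data are collected. The downside is that PFS and DOR may come out slightly shorter.

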**Table 7: Evaluation and Censoring of Progression-Free Survival**

Situation	Outcome	Date of Progression or Censoring
No baseline tumor assessments	Censored	Date of Day 1
No valid postbaseline response assessments	Censored	Date of Day 1
Progression documented between scheduled response assessments	Progressed	Date of first overall response of PD
No progression	Censored	Date of last valid radiologic assessment (not NE and not missing)
Study discontinuation for undocumented progression	Censored	Date of last valid radiologic assessment (not NE and not missing)
Study discontinuation for toxicity or other reason	Censored	Date of last valid radiologic assessment (not NE and not missing)
New anticancer treatment started	Censored	Date of last valid radiologic assessment (not NE and not missing) on/before starting a new anticancer treatment. (Date of PD assessment if the new anticancer treatment started after PD.)
Death before first progressive response assessment	Progressed	Date of death
Death between adequate response assessments	Progressed	Date of death
Death or progression after more than 1 missed assessment	Censored	Date of last valid radiologic assessment (not NE and not missing) before death

NE = not evaluable.

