- Duration of response, defined as the time from the earliest date of disease response (CR or PR) until earliest date of disease progression or death due to any cause, if occurring sooner than progression, will be determined by investigator assessment of radiographic disease assessments per RECIST v1.1 and mRECIST v1.1.
- DCR, defined as the percentage of subjects having CR, PR, or stable disease (SD), will be determined by investigator assessment of radiographic disease assessments per RECIST v1.1 and mRECIST v1.1.
- Duration of disease control (CR, PR, and SD) as measured from first report of SD or better until disease progression, will be determined by investigator assessment of radiographic disease per RECIST v1.1 and mRECIST v1.1, or death from any cause, if occurring sooner than progression.
- PFS, defined as the time from the start of combination therapy until the earliest date of disease progression or death due to any cause, if occurring sooner than progression, as determined by investigator assessment of objective radiographic disease assessments per RECIST v1.1 and mRECIST v1.1.
- OS determined from the start of combination therapy until death due to any cause. Survival analyses will occur at 1-year, 2-years, and at the end of the study.
- Safety and tolerability will be assessed by monitoring frequency, duration, and severity of AEs.

Overall Study Design:

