### 5.3.2.2. Phase 2 Response Evaluable Population

The Phase 2 response evaluable population includes all subjects enrolled in Phase 2 of the study who have received at least 1 dose of INCAGN01876, nivolumab, or ipilimumab; completed a baseline scan; and met at least 1 of the following criteria:

- $\geq 1$  postbaseline scan OR
- The subject has been on the study for a minimum of 64 days of follow-up OR
- The subject has discontinued from treatment.

[REDACTED]

[REDACTED]

[REDACTED]

[REDACTED]

[REDACTED]

[REDACTED]

[REDACTED]

[REDACTED]

[REDACTED]

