2.1.1.2	Summary of Unconfirmed Best Response Under RECIST v1.1 - by Treatment Group and Tumor Type	Phase 2 Response Population		X
2.2.1	Summary of Unconfirmed Best Response, Duration of Response, and Duration of Disease Control Under RECIST v1.1 - by Treatment Group and Dose	Phase 1 Response Evaluable Population		X
2.2.2	Summary of Unconfirmed Best Response, Duration of Response, and Duration of Disease Control Under mRECIST v1.1 - by Treatment Group and Dose	Phase 1 Response Evaluable Population		X
2.2.3.1	Summary of Confirmed Best Response, Duration of Response, and Duration of Disease Control Under mRECIST v1.1 - by Treatment Group and Tumor Type	Phase 2 Response Evaluable Population		X
2.2.3.2	Summary of Unconfirmed Best Response Under mRECIST v1.1 - by Treatment Group and Tumor Type	Phase 2 Response Evaluable Population		X
2.4.1	Summary of Progression-Free Survival Under RECIST v1.1	Phase 1 FAS Population		X
2.4.2	Summary of Progression-Free Survival Under RECIST v1.1 - by Tumor Type	Phase 2 FAS Population		X
2.5.1	Summary of Progression-Free Survival Under mRECIST v1.1	Phase 1 FAS Population		X
2.5.2	Summary of Progression-Free Survival Under mRECIST v1.1 - by Tumor Type	Phase 2 FAS Population		X
2.6.1	Summary of Overall Survival	Phase 1 FAS Population		X
2.6.2	Summary of Overall Survival - by Tumor Type	Phase 2 FAS Population		X

Table No.	Title	Population	Standard	In-Text
Safety				
3.1 Dose Exposure				
3.1.1.1	Summary of Drug Exposure to INCAGN01876 - by Treatment Group and Dose	Phase 1 FAS INCAGN01876 Population		X
3.1.1.2	Summary of Drug Exposure to INCAGN01876 - by Treatment Group and Tumor Type	Phase 2 FAS INCAGN01876 Population		X
3.1.2.1	Summary of Drug Exposure to Nivolumab - by Treatment Group and Dose	Phase 1 FAS Fixed Nivolumab Population		X
3.1.2.2	Summary of Drug Exposure to Nivolumab - by Treatment Group and Dose	Phase 1 FAS Weighted Nivolumab Population		X
3.1.2.3	Summary of Drug Exposure to Nivolumab - by Treatment Group and Tumor Type	Phase 2 FAS Fixed Nivolumab Population		X
3.1.2.4	Summary of Drug Exposure to Nivolumab - by Treatment Group and Tumor Type	Phase 2 FAS Weighted Nivolumab Population		X
3.1.3.1	Summary of Drug Exposure to Ipilimumab - by Treatment Group and Dose	Phase 1 FAS Ipilimumab Population		X
3.1.3.2	Summary of Drug Exposure to Ipilimumab - by Treatment Group and Tumor Type	Phase 2 FAS Ipilimumab Population		X

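### SAP Table 7 gives a subject who dies with no postbaseline scan two conflicting PFS outcomes, censored at Day 1 and event at death, and does not say which prevails

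*SAP*

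**What the plan says.** SAP 7.3.7 gives the definition: "Progression-free survival is defined as the length of time between the baseline visit (Day 1) and the earlier of death or PD". It then hands censoring to Table 7, which lists situations with an outcome and a date for each. Three rows matter here:

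- "No valid postbaseline response assessments": censored at Day 1.
- "Death before first progressive response assessment": event at the date of death.
- "Death or progression after more than 1 missed assessment": censored at the last valid scan before death.

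A further row, for subjects without a baseline tumor assessment, also censors at Day 1. Neither Table 7 nor SAP 7.3.7, 7.3.7.1 or 7.3.7.2 states an order of precedence.

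PFS is tabulated in the full analysis set. For Phase 2 this is SAP Appendix A, Table 2.4.2, "Summary of Progression-Free Survival Under RECIST v1.1 - by Tumor Type". Under SAP 5.3.1 that set holds every treated subject, scanned or not. For response, SAP 5.3.2.2 admits a treated subject with a baseline scan and no later one if "The subject has discontinued from treatment".

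Two neighbouring texts also bear on PFS. Protocol 5.6.3 treats palliative radiation as clinical progression for PFS, and Table 7 has no row for it. The endpoint lists (Protocol synopsis, Protocol 2.2.2, SAP 2.3.2) describe "PFS, defined as the time from the start of combination therapy until the earliest date of disease progression or death due to any cause" and "OS determined from the start of combination therapy until death due to any cause", whereas SAP 7.3.7 and 7.3.8 count from Day 1 and Cycle 1 Day 1.

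**The concern.** The two rows overlap for one kind of subject: treated, never scanned after baseline, and dead. One row places that subject at time zero with no event; the other places an event at the date of death. Two competent programmers could follow the SAP and produce different PFS curves from the same data.

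The difference runs in one direction only. Censoring the earliest deaths at Day 1 can only raise the curve. It would also treat one death in two ways within one report: a non-response in the response-evaluable denominator once treatment has ended, but no contribution to PFS. The row for a missing baseline scan has the same overlap with death.

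**Working it through.** **No stated figure to reproduce.** The documents give no PFS event count, median or power. The check is a comparison of rows, followed by an illustration of size.

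**Rows side by side.** Take a subject who has a baseline scan, is treated, and dies before Week 8, when the first on-study scan is due (Protocol 7.7.1.1.2).

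- No-postbaseline-scan row: condition met, censored at Day 1.
- Death row: condition met, event at death.
- Missed-assessment row: not met, because no scheduled scan has yet been missed.
- Definition in 7.3.7: event at death.

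Two rows apply with opposite outcomes, and the definition agrees with the death row.

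**Formula.** Let d of n subjects die before the first scan (8 x 7 = Day 56), with no other early censoring. At the first scan n - d subjects are at risk either way. Call the Kaplan-Meier product from then on P(t).

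- Deaths counted: S(t) = [(n - d)/n] x P(t).
- Deaths censored at Day 1: S(t) = P(t).
- Ratio, censored over counted: n/(n - d).

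**Inputs.** n = 46 and n = 57 are the smallest and largest full-enrolment sizes in Protocol Tables 19 and 20. Stage 1 sizes there run from 12 to 21. These are counts of evaluable subjects, used here as the cohort size for PFS. The value of d is an assumption.

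| n | d = 1 | d = 3 | d = 5 |
|---|---|---|---|
| 46 | 46/45 = 1.02 | 46/43 = 1.07 | 46/41 = 1.12 |
| 57 | 57/56 = 1.02 | 57/54 = 1.06 | 57/52 = 1.10 |

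At n = 46 a PFS of 40% would be reported too high by 40 x 0.022 = 0.9, 40 x 0.070 = 2.8 or 40 x 0.122 = 4.9 percentage points.

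**Cohorts stopped at Stage 1.** For the SCCHN doublet, n = 16: d = 1 gives 16/15 = 1.07 and d = 3 gives 16/13 = 1.23. Protocol Table 23 puts the chance of stopping there at 79.0% if the true response rate is 15%.

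**Coded Kaplan-Meier check.** Assumptions: n = 46, deaths at Week 5, about 40% of the rest progressing at Week 8 and about 35% of those remaining at each later 8-week scan.

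| d | Week 8 PFS, deaths counted | Week 8 PFS, censored at Day 1 | Median, counted / censored |
|---|---|---|---|
| 2 | 56.5% | 59.1% | Week 16 / Week 16 |
| 5 | 54.3% | 61.0% | Week 16 / Week 16 |
| 7 | 50.0% | 59.0% | Week 8 / Week 16 |
| 9 | 47.8% | 59.5% | Week 8 / Week 16 |

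The ratios follow n/(n - d). The median moves only where the curve is near 50% at a scan.

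**Reach.** SAP 7.3.3 applies the same censoring to duration of response, but a responder has a postbaseline scan by definition, so the overlap cannot arise there.

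**The case against.** The strongest reply is that the intended reading can be recovered. SAP 7.3.7, 7.3.7.1 and 7.3.7.2 each end PFS at death or progression, and Table 7 has a specific row making such a death an event. Other general rows, such as the one for no progression, also literally fit subjects who later die without progression. The table therefore works only if its death rows override its censoring rows. This stands as far as it goes. A reader might infer that the SAP as written removes early deaths and so overstates PFS; the documents do not support that, because the death row counts the same subjects and the definition favours it. What remains is that 7.3.7 delegates censoring to the table, the Day 1 row is unconditional and comes earlier, and nothing tells the programmer to skip it.

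A second reply is that the size is assumed. This stands too: no early-death rate is documented, and a shift in the median needs a curve close to 50% at a scan.

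A reader might also infer that PFS and OS in the sequenced groups (B, E, H and L) have two start dates 28 days apart (2 x 14-day cycles), because the partner drugs begin at Cycle 3. The endpoint lists do leave their starting phrase undefined. However, SAP 7.3.7 and 7.3.8, with 4.1.1 and 4.1.6, fix one origin at the first dose of any study drug. That is a wording note, not a second analysis problem.

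On radiation, Table 7 does not say that palliative radiation belongs under its new-treatment row, and Protocol 5.6.3 allows it only exceptionally, so few subjects are concerned. The mismatch is still real: the protocol states a PFS rule that the SAP table lacks, while SAP 10.1 reports no changes to protocol-defined analyses.

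**Conclusion.** The conflict in Table 7 is real and should be resolved. A death with no valid postbaseline scan has two prescribed outcomes and no ranking, and only the event agrees with the SAP's own definition. Bias arises only if the Day 1 row is applied first. The curve is then too high by n/(n - d): 1.02 to 1.12 for one to five such deaths in a fully enrolled cohort of 46, and more in a cohort stopped at Stage 1. These figures rest on an assumed d and on no other early censoring.

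The consequence is confined to descriptive, single-arm secondary PFS estimates. Primary ORR, the Simon designs and type I error are unaffected. The radiation mismatch is minor.

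**What to change.** 1. In SAP Table 7, limit both Day 1 censoring rows (no baseline assessment, and no valid postbaseline assessment) to subjects who did not die before the second scheduled scan.
2. Count a death before that scan as an event at the date of death, unless new anticancer treatment was started first. In that case the existing new-treatment row applies.
3. Leave later deaths with no scan under the existing row "Death or progression after more than 1 missed assessment". The boundary is consistent with it: before the second scan at most one assessment can have been missed.
4. Minor: reconcile Protocol 5.6.3 with Table 7 so that a single rule for palliative radiation governs PFS.
5. Wording note: in the Protocol synopsis, Protocol 2.2.2 and SAP 2.3.2, align the starting phrase for PFS and OS with the Day 1 / Cycle 1 Day 1 origin already used in SAP 7.3.7 and 7.3.8.

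The cost is text in the SAP and in the protocol's endpoint and radiation wording. No new data are needed and the sample size does not change.

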#### **7.3.3. Duration of Response**

Duration of response will be assessed with RECIST v1.1 and mRECIST v1.1 criteria.

Censoring of DOR will follow the same algorithm as the censoring of PFS (as described in Section 7.3.7). Kaplan-Meier curves for DOR will be presented by cohort-specific tumor types. The KM estimate of median DOR will be presented with its 95% CI. The 95% CI will be calculated using Brookmeyer and Crowley's method ([Brookmeyer and Crowley 1982](#)). A swim plot for DOR will be generated under both RECIST v1.1 and mRECIST v1.1 criteria.

Duration of response as assessed by RECIST v1.1 and mRECIST v1.1 will be summarized by treatment group and dose level for the Phase 1 response evaluable population and by treatment group and tumor type for the Phase 2 response evaluable population.

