**7.3.7.1. Progression-Free Survival by RECIST v1.1**

Under RECIST v1.1, PFS is defined as the length of time between the baseline visit (Day 1) and the earlier of death or first assessment of PD as assessed by RECIST v1.1.

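### SAP Table 7 labels a documented progression as censored when new anticancer therapy follows it, which contradicts the SAP's own PFS definition and carries into DOR

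*SAP*

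**What the plan says.** SAP Section 7.3.7: "Progression-free survival is defined as the length of time between the baseline visit (Day 1) and the earlier of death or PD". Section 7.3.7.1, for RECIST v1.1, ends PFS at "the earlier of death or first assessment of PD as assessed by RECIST v1.1". Neither depends on what treatment follows, and nor does the endpoint definition in Protocol Section 2.2.2.

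Section 7.3.7 then states: "Censoring for PFS will follow the algorithm outlined in" Table 7. The rows that matter here are:

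- "New anticancer treatment started". The only outcome is Censored. The date is the last valid scan on or before the start of the new treatment, followed by a parenthesis: "Date of PD assessment if the new anticancer treatment started after PD".
- "Progression documented between scheduled response assessments". The outcome is Progressed. This is the only row that codes a radiological PD as an event.
- Two death rows, one of them "Death before first progressive response assessment", are also Progressed.
- Death or PD after more than one missed assessment is Censored.

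For mRECIST, Section 7.3.7.2 refers to Table 6. There, starting new anticancer therapy in the 4- to 6-week window after an unconfirmed PD makes that PD count as confirmed.

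For DOR, Section 7.3.3 says: "Censoring of DOR will follow the same algorithm as the censoring of PFS". Section 7.3.3.1 ends DOR at death or first PD.

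**The concern.** The parenthesis brings subjects who have already progressed into a row whose outcome is Censored. It changes their date but not their status. A programmer who builds the event flag from the outcome column would censor these subjects on their PD date, and no other row clearly restores the event.

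Censoring at the moment of progression is informative in the worst way: the subject leaves the risk set at exactly the point where the event occurred. Kaplan-Meier PFS and DOR would be too long. The error would also vary between cohorts with access to next-line therapy, so cohorts would differ for a reason unrelated to study treatment.

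**Working it through.** The documents give no PFS or DOR median, event count or power, so there is no stated figure to reproduce. The check is a reading of the rows, followed by an illustration of scale.

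**Row check.** Take PD at the scheduled Week 8 scan and new therapy at Week 11, with no missed scans.

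| Rule | Result |
|---|---|
| SAP 7.3.7 and 7.3.7.1 | Event at Week 8 |
| Table 7, progression row | No match: the PD was at a scheduled scan, not between scans |
| Table 7, new-treatment row | Match: Censored, dated Week 8 |

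Now move the PD between scheduled scans. The progression row gives Progressed and the new-treatment row gives Censored, both on the PD date. Table 7 does not say which prevails.

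For mRECIST, take an unconfirmed PD at Week 8 and new therapy at Week 13. That is 13 − 8 = 5 weeks later, inside the 4- to 6-week window. Table 6 confirms the PD; Table 7's new-treatment row says Censored.

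**PD at a scheduled scan with no later therapy.** Imaging is at Week 8 and then every 8 weeks for 12 months (Protocol Table 10), so such PDs will occur. They match neither the progression row nor any censoring row. Sections 7.3.7 and 7.3.7.1 still make them events. This is a gap in the table, not an instruction to censor.

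**Scale if the new-treatment row is programmed literally.** Both inputs are assumptions:

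- s = share of PFS events that are PD, taken as 0.85.
- f = share of progressors with a recorded start of new therapy, taken as 0.25 to 0.60.

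The share of PD events lost is f. The share of all PFS events lost is g = s × f. With exponential PFS and loss unrelated to the timing of PD, the hazard estimate is multiplied by (1 − g), so the median is multiplied by 1/(1 − g).

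| f | g = 0.85 × f | 1/(1 − g) |
|---|---|---|
| 0.25 | 0.2125 (21%) | 1.27 |
| 0.40 | 0.340 (34%) | 1.52 |
| 0.50 | 0.425 (43%) | 1.74 |
| 0.60 | 0.510 (51%) | 2.04 |

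**Cross-check by simulation**, also on assumed inputs: 200,000 subjects, true median 4.0 months, follow-up 12 to 24 months, s of 0.80 to 0.90. The Kaplan-Meier median became 4.7 to 4.9 months at f = 0.20, 5.9 to 6.3 at 0.40, 7.7 to 8.7 at 0.60, and 11.1 to 14.1 at 0.80. The formula agrees: for s = 0.80 and f = 0.40, 4.0/(1 − 0.32) = 5.88, against 5.87 simulated. With these PDs counted as events, the median stays at 4.0.

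**The case against.** The strongest reply is that the table intends an event. The date column covers both progression and censoring dates, and the parenthesis sets apart therapy started after PD and gives it the PD date. Read with Sections 7.3.7 and 7.3.7.1, that is a progression date, and Table 6 points the same way for mRECIST. On this view the outcome cell is a labelling slip and a careful programmer would follow the definition. Much of this stands: the SAP does not show a deliberate plan to censor progressors. But the outcome cell still says Censored, Section 7.3.7 makes Table 7 the censoring algorithm, and neither the SAP nor Protocol Section 9.4.1.2 says which text prevails.

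A reader might infer more: that most progressors drop out as events, or that PD at a scheduled scan is censored. The documents do not support either. Losing most progressors through the new-treatment row requires more than half of them to start new therapy, and no such share is given. Censoring scheduled-scan PD requires Table 7 to be exhaustive and to override the definition, and the SAP says neither.

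It is also fair that PFS and DOR are secondary and are estimated without a hypothesis test. The primary ORR, the Simon boundaries and the Bayesian futility rule do not use Table 7.

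**Conclusion.** The contradiction is real and should be corrected before PFS and DOR are programmed. It is best described as a wrong or incomplete outcome label plus a missing row. The direction is certain if the new-treatment row is followed literally: true events are lost and PFS and DOR lengthen. The size is not known from the documents. The range of 21% to 51% of PFS events lost, and a median inflated 1.27- to 2.04-fold, rests on an assumed 85% PD share, an assumed 25% to 60% starting new therapy, and exponential PFS. If the programmer follows the definition instead, nothing is lost. It should therefore not be inferred that every cohort's estimates will be too long. The consequence is confined to secondary endpoints.

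**What to change.** Amend SAP Table 7 as follows:

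- Split the new-treatment row. (a) New anticancer treatment started before PD or death: Censored, at the last valid assessment on or before its start. (b) PD on or before the start of new anticancer treatment: Progressed, at the date of first PD, using PD confirmed per Table 6 for mRECIST.
- Reword the progression row to cover PD documented at or between scheduled assessments: Progressed.
- State that the row censoring death or progression after more than one missed assessment takes precedence over these rows. Without that, a late PD would match two opposite outcomes.
- State in Section 7.3.3 that the same rules and precedence apply to DOR.

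The cost is SAP wording and the matching program specification. No new data are needed.
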